**Table 4-1: Allowable ranges for continuous efficacy variables**

Variable	Minimum	Maximum
MASES	0	13
PASI	0	72
LDI	0	NA
DAS28(CRP)	0.988 a	NA
CRP b	0.08	NA
PsAID-9	0	10
SF-36 MCS	-3.33	80.09
SF-36 PCS	5.02	79.78
HADS-A	0	21
HADS-D	0	21
TJC	0	78
SJC	0	76
HAQ-DI	0	3
PtAAP	0	100
PhGADA	0	100
PGADA	0	100

CRP=high sensitivity C-reactive protein; DAS28(CRP)=Disease Activity Score 28 joint count C-reactive protein; HADS-A=Hospital Anxiety and Depression Scale – Anxiety; HADS-D=Hospital Anxiety and Depression Scale – Depression; HAQ-DI=Health Assessment Questionnaire - Disability Index; LDI=Leeds Dactylitis Index; LLOQ=lower limit of quantification; MASES=Maastricht Ankylosing Spondylitis Enthesitis Index; NA=not applicable; PASI=Psoriasis Area and Severity Index; PGADA=Patient’s Global Assessment of Disease Activity; PhGADA=Physician’s Global Assessment of Disease Activity; PsAID-9=Psoriatic Arthritis Impact of Disease-9; PtAAP=Patient's Assessment of Arthritis Pain; SF-36 MCS=Short Form 36-Item – Mental Component Summary; SF-36 PCS=Short Form 36-Item – Physical Component Summary; SJC=swollen joint count; TJC=tender joint count.

a For the purpose of the analysis, the actual minimum value will be set to the calculated value of  $0.36 \cdot \ln(\text{CRP}+1) + 0.96$  using the minimum CRP of 0.08mg/L.

b For the purpose of the MI any numerical CRP values obtained in PA0009 that were <0.16 mg/L will be substituted with half the lower limit of quantification (LLOQ) LLOQ from PA0008 (ie, 0.08 mg/L) prior to performing the MI. Subsequently any imputed values of <0.16mg/L will be replaced by the value of 0.08mg/L for the purpose of summaries based on imputed data. Listings will display the original result. Any CRP values of  $\geq 500$ mg/L will be

set to missing prior to performing the MI procedure; the subsequently imputed CRP value will be included in the summary tables.

### Step 3 (Excluding CRP)

The 100 imputed datasets will be combined, and simple means and standard errors will be calculated using Rubin's rules (via SAS® PROC MIANALYZE). For calculation of other descriptive statistics (median, minimum and maximum), Rubin's rules do not apply. Multiple imputation estimates will be computed by calculating arithmetic means of the estimates from the multiple repetitions of the imputation algorithm. Thus, for median, minimum and maximum the following approach will apply:

- The data will be summarized by treatment, visit and imputation and the summary statistics will be computed.
- Results will be summarized by taking the mean value of each summary statistic at each visit across all imputations.

The number of decimal places will remain the same as the original for display purposes (ie, if the mean was presented to 1 decimal place, the mean of the means will also be presented to 1 decimal place).

### Step 3 (CRP only)

The CRP data will be presented using the geometric mean, 95% confidence interval (CI) for the geometric mean, median, Q1, Q3, minimum and maximum. The change from Baseline will be expressed as the ratio to Baseline in the summaries. The following approach will be applied:

- Following the MI procedure the ratio to Baseline will be calculated for any of the imputed values
- The natural logarithm of the absolute values and of the ratios to Baseline will be calculated
- The logged values will be summarized by treatment, visit and imputation
- The datasets will be combined using PROC MIANALYZE in order to get the mean and 95% CI estimates from the absolute values and ratios to Baseline (based on logged data) across imputations
- The estimates of the mean and 95% CI will be back-transformed to obtain the geometric mean and 95% CI on the original scale
- For the median, Q1, Q3, minimum and maximum the procedure outlined above for the other endpoints will be followed

As a sensitivity analysis, certain efficacy variables will be summarized based on observed data (see [Section 8](#)).

As a further sensitivity analysis for ACR and PASI responses, the response variables will be derived following MI of the individual components for ACR or following MI of the overall PASI score. The ACR and PASI responses will then be derived for each subject and each imputation (where each imputation is performed across all individual components for ACR) and the number and percentage of subjects with each ACR and PASI response in each imputation will be

calculated. The mean value (across imputations) for the percentage of subjects with each ACR or PASI response will be reported.

A similar approach will be followed for the calculation and summary of the number and percentage of subjects with normal HADS scores (defined as having HADS-D and HADS-A <8 at the same visit) based on the HADS-D and HADS-A values after MI.

Primary and sensitivity analyses are summarized in Table 4–2. All summaries presenting data following MI will include only visits from PA0009 EV onwards (although the MI procedure will incorporate data from both PA0008 and PA0009).

**Table 4–2: Missing data handling**

Variable	Type	Missing data handling approach		
		NRI	MI/MCMC (monotone regression)	OC
ACR20, 50, 70	Responder	P	S a	S
MASES	Continuous		P	S
LDI	Continuous		P	S
PASI75, 90, 100	Responder	P	S a	S
MDA	Responder	P		S
DAS28 (CRP)	Continuous		P	
CRP	Continuous		P	
PsAID-9	Continuous		P	
SF-36 PCS, MCS	Continuous		P	
HADS-A, HADS-D	Continuous		P	
Incidence of normal depression/anxiety status (using HADS)	Responder		P a	
TJC, SJC	Continuous		P	
HAQ-DI	Continuous		P	
PtAAP	Continuous		P	
PGADA	Continuous		P	
PhGADA	Continuous		P	

ACR=American College of Rheumatology 20, 50, 70% response criteria; CRP=high sensitivity C-reactive protein; DAS28(CRP)=Disease Activity Score 28 joint count C-reactive protein; HADS-A=Hospital Anxiety and Depression Scale – Anxiety; HADS-D=Hospital Anxiety and Depression Scale – Depression; HAQ-DI=Health Assessment Questionnaire - Disability Index; LDI=Leeds Dactylitis Index; LLOQ=lower limit of quantification; MASES=Maastricht Ankylosing Spondylitis Enthesitis Index; MCMC=Markov-Chain Monte Carlo; MDA=Minimal Disease Activity; MI=multiple imputation; NRI=nonresponder imputation; OC=observed case; P=primary method; PASI 75, 90, 100=Psoriasis Area and Severity Index 75%, 90% and 100%; PGADA=Patient’s Global Assessment of Disease Activity; PhGADA=Physician’s Global Assessment of Disease Activity; PsAID-9=Psoriatic Arthritis Impact of Disease-9; PtAAP=Patient’s Assessment of Arthritis Pain; S=secondary method;

SF-36 MCS=Short Form 36-Item – Mental Component Summary; SF-36 PCS=Short Form 36-Item – Physical Component Summary; SJC=swollen joint count; TJC=tender joint count.

a Imputation method is applied on continuous data, and response variable is derived from the continuous data based on complete dataset.

In the event that the MI model fails to converge or will not run for other reasons (eg, data issues, data distribution), alternative approaches may be considered including LOCF and /or OC summaries as appropriate. For some efficacy endpoints, these approaches may be planned already as part of the existing analyses or sensitivity analyses, and therefore it may not be necessary in all cases to provide additional summaries.

#### **4.2.2 Additional rules for handling missing data for derivation of PASI response**

Supplementary supporting analyses will be performed for the PASI response in order to take into account missing PASI data during the study. PASI data are known to be missing for some subjects/visits due to an error in the original protocol schedule of events which stated that PASI would only be determined at a given visit if the BSA affected by psoriasis at that visit was  $\geq 3\%$ . The protocol was subsequently updated (Amendment 3) to correct the schedule of events such that PASI is assessed at all visits for subjects with BSA affected by psoriasis of  $\geq 3\%$  at PA0008 Baseline.

These supporting analyses will be performed in addition to those described in [Section 4.2.1](#) and will utilize the BSA assessments to provide surrogate information regarding the PASI response. Two different approaches will be used in this regard:

- For any visit where the derived total PASI score is missing the subject will be considered as a PASI responder if the corresponding BSA assessment at the same visit is 0%. A BSA of 0% will therefore be considered to meet the criteria for PASI75, PASI90, and PASI100 responses.
- For any visit where the derived total PASI score is missing, the PASI response will be imputed using LOCF (based on OC data) only if the BSA has not worsened at any interim time point or the current time point compared to the last visit at which both PASI response and BSA were non-missing (including unscheduled/repeat assessments).

For example, if the PASI score is missing at Visit 4 (Week 12), the response (PASI75, PASI90, or PASI100) at Visit 1 EV will be carried forward and used in the summary, if BSA at Visit 4  $\leq$  BSA at Visit 1. If BSA at Visit 4  $>$  BSA at Visit 1, the response will be left as missing.

- If the data at the PA0009 EV are missing the LOCF will be taken from the last available assessment obtained in PA0008 (based on OC data).
- The approach above will be followed regardless of the BSA value at the corresponding visit, ie, if the BSA=0% at the visit, the previous PASI response will be carried forward for each variable (PASI75, PASI90, and PASI100) and may be Yes or No.

For both approaches above, the rules will be applied to PA0009 data only and only for subjects in the FAS. In addition, this will be implemented only for subjects with BSA  $\geq 3\%$  at PA0008 Baseline.

### 4.2.3 Handling of missing data for adverse events

A complete date must be established to correctly identify the AE as treatment-emergent. For purposes of imputing missing components of partially reported start and stop dates for AEs, the algorithms listed below will be followed. Start and stop dates of AEs will be displayed as reported in the subject data listings (ie, no imputed values will be displayed in data listings).

Partial or missing start dates for events recorded during PA0008 (including those which were ongoing at the start of PA0009) will be imputed using the imputed start date from the PA0008 database.

Imputation of partial AE start dates for events reported in PA0009 only will follow the rules below (treatment switching rules refer to PA0008 only and data were used directly from the PA0008 database):

- If only the month and year of the AE start date are specified, and the month and year of the start date of study medication in PA0009 are not the same as the month and year of the AE start date, and the subject did not switch treatment during that month and year, then use the 1st of the month of the AE start date.
- If only the month and year of the AE start date are specified, and the month and year of the start date of study medication in PA0009 are not the same as the month and year of the AE start date, and the subject switched treatment during the month and year of the AE start date, then use the date of treatment switch.
- If only the month and year of the AE start date are specified, and the month and year of the start date of study medication in PA0009 are the same as the month and year of the AE start date, then use the start date of study medication in PA0009 (regardless of treatment switching). If this results in a start date after a known end date use the 1st of the month of the AE start date.
- If only the year of the AE start date is specified, and the year of the start date of study medication in PA0009 is not the same as the year of the AE start date, and the subject did not switch treatment during the year of the AE start date, then use the 1st of January of the year of the AE start date.
- If only the year of the AE start date is specified, and the year of the start date of study medication in PA0009 is not the same as the year of the AE start date, and the subject switched treatment during the year of the AE start date, then use the date of treatment switch.
- If only the year of the AE start date is specified, and the year of the start date of study medication in PA0009 is the same as the year of the AE start date, then use the start date of study medication in PA0009 (regardless of treatment switching). If this results in a start date after a known end date use the 1st of January of the year of the AE start date.
- If only the year and day of the AE start date are specified, and the year of the start date of study medication in PA0009 is not the same as the year of the AE start date, then use January of the year of the AE start date together with the known day.
- If only the year and day of the AE start date are specified, and the year of the start date of study medication in PA0009 is the same as the year of the AE start date, then use the start month of study medication in PA0009 together with the known day.

- If this results in a start date after a known end date use January of the year of the AE start date together with the known day.
- If this results in a start date prior to the start date of study medication in PA0009 (in the imputed month) the event will be considered to be treatment-emergent.
- If the AE start date is completely unknown and the AE stop date is unknown or not prior to the start date of study medication in PA0009, then use the start date of study medication in PA0009.

Imputation of partial AE stop date:

- If only the month and year of the AE stop date are specified, then use the last day of that month and that year.
- If only the day and year are specified, then use December of that year
- If only the year of the AE stop date is specified, then use December 31st of that year.
- If the AE stop date is completely unknown, do not impute the stop date.

In the event of ambiguity or incomplete data which makes it impossible to determine whether the AE was treatment-emergent, the AE will be considered treatment-emergent. For subjects who may have died during the study, imputed dates will be truncated at the date of death.

If the intensity of an AE is unknown, it is considered as severe. If the relationship to study drug is missing, it is considered as related.

If the seriousness of an AE is unknown, no imputation will be performed. Such events will therefore be excluded from any listings or summaries of SAEs.

#### **4.2.4 Handling of missing data for prior and concomitant medication**

A complete start and stop date must be established to correctly identify the medication as prior or concomitant. For purposes of imputing missing components of partially reported start and stop dates for medications, the algorithms listed below will be followed. Start and stop dates of medications will be displayed as reported in the subject data listings (ie, no imputed values will be displayed in data listings).

Partial start dates for medications which started during PA0008 and were ongoing at the start of PA0009 will be taken from the PA0008 database based on the dedicated eCRF page for imported medications in PA0009.

Imputation of all partial start dates for medications (including those reported on the 'imported' page) will follow the rules below (treatment switching rules refer to PA0008 only):

- If only the month and year of the medication start date are specified, and the month and year of the start date of study medication in PA0009 are not the same as the month and year of the medication start date, and the subject did not switch treatment during that month and year, then use the 1st of the month of the medication start date.
- If only the month and year of the medication start date are specified, and the month and year of the start date of study medication in PA0009 are not the same as the month and year of the medication start date, and the subject switched treatment during the month and year of the medication start date, then use the date of treatment switch.

- If only the month and year of the medication start date are specified, and the month and year of the start date of study medication in PA0009 are the same as the month and year of the medication start date, then use the start date of study medication in PA0009 (regardless of treatment switching). If this results in a start date after a known end date use the 1st of the month of the medication start date
- If only the year of the medication start date is specified, and the year of start date of study medication in PA0009 is not the same as the year of the medication start date, and the subject did not switch treatment during the year of the medication start date, then use the 1st of January of the year of the medication start date.
- If only the year of the medication start date is specified, and the year of the start date of study medication in PA0009 is not the same as the year of the medication start date, and the subject switched treatment during the year of the medication start date, then use the date of treatment switch.
- If only the year of the medication start date is specified, and the year of the start date of study medication in PA0009 is the same as the year of the medication start date, then use the start date of study medication in PA0009 (regardless of treatment switching). If this results in a start date after a known end date use the 1st of January of the year of the medication start date.
- If only the year and day of the medication start date are specified, and the year of the start date of study medication in PA0009 is not the same as the year of the medication start date, then use January of the year of the medication start date together with the known day.
- If only the year and day of the medication start date are specified, and the year of the start date of study medication in PA0009 is the same as the year of the medication start date, then use the start month of study medication in PA0009 together with the known day.
  - If this results in a start date after a known end date use January of the year of the medication start date together with the known day.
  - If this results in a start date prior to the start date of study medication in PA0009 (in the imputed month) the medication will be considered to be concomitant.
- If the medication start date is completely unknown and the medication stop date is unknown or not prior to the start date of study medication in PA0009, then use the start date of study medication in PA0009.

Imputation of partial medication stop dates:

- If only the month and year of the medication stop date are specified, then use the last day of that month and that year.
- If only the day and year are specified, then use December of that year
- If only the year of the medication stop date is specified, then use December 31st of that year.
- If the medication stop date is completely unknown, do not impute the stop date.

In the event of ambiguity or incomplete data which makes it impossible to determine whether the medication was prior or concomitant, the medication will be considered concomitant. For

subjects who may have died during the study, imputed dates will be truncated at the date of death.

There will be no imputation of any other missing data for concomitant medications.

#### 4.2.5 Handling of partial treatment end dates

The date of last study drug administration in PA0009 may be completely unknown (eg, if the subject is lost to follow-up) or partially known. In the latter case, it is possible to enter a known month and year into the database but to leave the day as missing (ie, YYYY-MMM-XX) on the study termination page of the eCRF.

Missing or partial treatment end dates will be handled according to the following rules:

- For subjects for whom the treatment end date is completely missing on the study termination page, the date of last dose in PA0009 will be the date/time of the last known dose as reported on the study medication administration page of the eCRF.
- For subjects for whom the treatment end date is partially missing (ie, only the month and year are known) the following rules will be applied:
  - The treatment end date will be imputed as date of last known study medication administration + 28 days (ie, equivalent to the dosing interval), assuming this gives an imputed date in the known month and year
  - If the above rule results in an imputed date that is not in the known month and year the following will apply:
    - If the date of last known study medication +28 days results in a month PRIOR to the month of the partial date, then the imputed date of last dose will be set to the 1st of the known month ie, YYYY-MMM-01.
    - If the date of last known study medication +28 days results in a month AFTER the month of the partial date, then the imputed date of last dose will be set to the last day of the known month eg, YYYY-MM-31 (modified according to the calendar month).

In the listings the date of last study drug administration will be displayed as received in the data ie, without imputation.

### 4.3 Interim analyses and data monitoring

No formal interim analysis is planned for this study. Additional data cuts may be prepared following regulatory requests or for publication purposes.

A snapshot of data will be taken after the final subject has reached PA0009 Week 60 and used to create displays in this SAP, based on one year's exposure in the study. No change to study conduct is expected as a result.

### 4.4 Multicenter studies

The data from all centers will be pooled for the purposes of analysis. There will be no formal statistical evaluation of the effect of center on the results obtained.

Centers will be grouped into the geographic regions of North America and Europe as described in [Section 3.8](#) for use as a covariate in statistical analyses and for subgroup analyses.

#### **4.5 Multiple comparisons/multiplicity**

Not applicable.

#### **4.6 Use of an efficacy subset of subjects**

Not applicable.

#### **4.7 Active-control studies intended to show equivalence**

Not applicable.

#### **4.8 Examination of subgroups**

Subgroup summaries of the efficacy variables of ACR20, ACR50, ACR70 and PASI75 and PASI90 response at PA0009 Week 48 will be performed. The following subgroups will be used:

- Geographic region at PA0008 Baseline (North America, Europe), as defined in [Section 3.8](#).
- Previous (past) TNF inhibitor agent exposure in PA0008. The value in the PA0008 database for past anti-TNF therapy (as collected on the eCRF) will be used for PA0009, without additional derivation.
- Disease duration at start of PA0008 (<2 years, ≥2 years). The value in the PA0008 database will be used for PA0009, without additional derivation.
- Concomitant DMARD status at start of PA0008 (yes, no). The value in the PA0008 database will be used for PA0009, without additional derivation.

### **5 STUDY POPULATION CHARACTERISTICS**

#### **5.1 Subject disposition**

Subject disposition (date of first and last subject visit, number of subjects included in each analysis set [ES, SS, and FAS]) will be presented overall, by region and for each site, and by treatment group at completion of PA0008 and overall for the ES.

The number and percentage of subjects in each analysis set (ES, SS and SS Sub-populations, and FAS) will be presented by treatment group at completion of PA0008 and overall.

The number and percentage of subjects who started, completed and discontinued the study, along with the primary reason for discontinuation will be presented by treatment group at completion of PA0008 and overall for the SS (a subject will be considered to have completed the study if they attended Visit 13 [Week 104]). For the purposes of the summaries the data will be taken directly from the eCRF page for study termination.

The number and percentage of subjects who started, completed and discontinued study medication, along with the primary reason for medication discontinuation will be presented by treatment group at completion of PA0008 and overall for the SS (a subject will be considered to have completed study treatment if they received a dose at Visit 12 [Week 100]). For the purposes of the summaries the data will be taken directly from the eCRF page for study medication discontinuation.

For any subjects where the data on the study termination and study medication discontinuation eCRF pages are inconsistent, the data reported on the study termination page will be considered

as primary ie, if a subject is reported as discontinuing from the study, they will be regarded as discontinuing study medication as well (regardless of whether this is reported in the eCRF).

Discontinuations due to AEs will be summarized by treatment group at completion of PA0008 and overall for the SS.

Subjects who did not meet the eligibility criteria and the inclusion and/or exclusion criteria not met will be listed for the ES.

Subject disposition (subject status, date of informed consent, date of enrollment into PA0009, treatment sequence across PA0008 and PA0009, treatment received at the completion of PA0008, start and end date/time and relative days of study medication in PA0009, date of premature study discontinuation and date of final contact) will be listed for the ES. Days relative to the start date of study medication in PA0008 and to the start of study medication in PA0009 will be included for the end date of study medication.

Subject inclusion in each analysis set will be listed for the ES.

Subjects excluded from at least 1 analysis set, with reason for exclusion, will be listed for the ES. Subjects who were excluded from the SS will have a reason of ‘Subject did not receive at least one dose of study medication during PA0009’, and subjects who were excluded from the FAS will have a reason of ‘Subject did not have a valid measurement of at least one efficacy variable after PA0009 study entry’.

Study and treatment discontinuation reasons and the name of any subsequent treatment will be listed for the ES. Total days on study medication from the start date in PA0008 and from the start date in PA0009 will be included. These will be calculated as described below:

$$\begin{aligned} & \textit{Total days on study medication from start date in PA0009} \\ & = (\textit{Date of last dose in PA0009} - \textit{Date of first dose in PA0009}) + 1 \end{aligned} \quad (6)$$

$$\begin{aligned} & \textit{Total days on study medication from start date in PA0008} \\ & = (\textit{Date of last dose in PA0009} - \textit{Date of first dose in PA0008}) + 1 \end{aligned} \quad (7)$$

For the total days on study medication in PA0008 this will be calculated from the first dose of any medication received regardless of treatment assignment.

Visit dates, including the day relative to the start of study medication in PA0008 and in PA0009, will be listed for the ES.

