## 7 MEASUREMENTS OF TREATMENT COMPLIANCE

Compliance will be summarized using the number of doses received relative to the number of doses expected:

$$\text{Percent treatment compliance} = 100 * \frac{\text{Number of doses received}}{\text{Number of doses expected}} \quad (10)$$

where the total number of expected doses is derived relative to when the subject finishes treatment. If a subject completes treatment 26 doses are expected (EV and every fourth week afterwards until PA0009 Week 100). If a subject discontinues early, then the number of expected doses is based on the time of study discontinuation relative to the planned dosing visits (taking into account the permitted visit window). If the date of study discontinuation is missing the final contact date (as reported on the eCRF) will be used instead.

A summary of percent treatment compliance, both continuous and categorized as  $\leq 75\%$  and  $>75\%$ , will be provided by treatment group at completion of PA0008 and overall for the SS.

Treatment compliance will be listed for the SS. A separate listing of study medication administration (including injection dates and times, kit numbers, who performed the injection and the location of the injection) will be presented.

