## 12.6 COVID-19 data collection

For study visits impacted by COVID-19, additional data will be collected on a separate dedicated eCRF page.

The following information will be reported:

- Specification of the impacted visit (eg, Visit 5)
- Date of the impacted visit
- Category of the impact (multiple categories may apply to the same visit)
  - Visit not done
  - Visit performed out of window
  - Home visit
  - Visit performed by video call
  - Visit performed by telephone
  - Investigational product shipped to study participant
  - Home administration of investigational product by participant or caregiver
  - Home administration of investigational product by a healthcare professional
  - Missed study drug administration/dispensation

- Temporary discontinuation of study drug
- Permanent discontinuation of study drug
- Termination of study participation
- Other
- Relationship to COVID-19
  - Confirmed COVID-19 infection
  - Suspected COVID-19 infection
  - General circumstances around COVID-19 without infection
  - Other

A narrative of the event will also be collected.

This document cannot be used to support any marketing authorization application and any extensions or variations thereof.

REDACTED COPY

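### The override in SAP 5.1 can count a subject who received the Week 100 dose, and so completed treatment, as having discontinued study medication

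*SAP*

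**What the plan says.** SAP 5.1 sets two separate milestones. For medication, "a subject will be considered to have completed study treatment if they received a dose at Visit 12 [Week 100]". For the study, "a subject will be considered to have completed the study if they attended Visit 13 [Week 104]". Both disposition tables take their data directly from the corresponding eCRF page, and each reports a primary reason for discontinuation.

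The section then adds a tie-break. It opens with "For any subjects where the data on the study termination and study medication discontinuation eCRF pages are inconsistent", makes the study termination page primary, and explains what that means: "if a subject is reported as discontinuing from the study, they will be regarded as discontinuing study medication as well". It closes with "regardless of whether this is reported in the eCRF". The date of the last dose plays no part in the rule.

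SAP 7 says "If a subject completes treatment 26 doses are expected", the last of them at Week 100. No dose is planned at Week 104 (protocol Table 5-1 and SAP Table 2-1).

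**The concern.** The two milestones are four weeks apart, so having completed treatment but discontinued the study is a legitimate status under the SAP's own definitions. The override removes that status. A subject dosed at Week 100 whose termination page records discontinuation moves to the discontinued row of the medication table, where a primary reason is expected although no planned dose was left to stop.

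At stake is one descriptive output in a study whose primary objective is long-term safety and tolerability. The share of subjects who completed about two years of treatment will be read as part of that description, and the table would contradict both the stated completer definition and the compliance output.

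**Working it through.** **Inputs**
- Dosing: entry visit, then every 4 weeks to Week 100 (SAP 7; SAP Table 2-1).
- Milestones: Visit 12 dose for treatment, Visit 13 attendance for the study (SAP 5.1).
- Compliance: 100 × doses received / doses expected. For an early leaver, the expected doses are those planned up to study discontinuation (SAP 7, formula 10).
- Visit window: ±7 days around Visits 12 and 13 (SAP Table 2-1, footnote a).
- Ceiling on enrollment: 200 (SAP 2.4).
- Number of subjects who leave after the Week 100 dose: not given, so assumed below.

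**Step 1: the plan's own figure.** 100/4 + 1 = 26 doses. This reproduces SAP 7 and equals the number of weeks marked for administration in the schedule.

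**Step 2: one subject through the rules.** Take a subject who receives every dose and withdraws at Week 102.

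| Rule | Result |
|---|---|
| Treatment completion, SAP 5.1 | Visit 12 dose given: completed |
| Study completion, SAP 5.1 | Visit 13 not attended: not completed |
| Compliance, SAP 7 | 26 doses planned by Week 102; 100 × 26/26 = 100% |
| Override, SAP 5.1 | Study discontinued, so medication discontinued |

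Withdrawal at Week 101 or Week 103 gives the same four results. The last row contradicts the first and does not fit the third.

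**Step 3: the window.** Nominally 104 − 100 = 4 weeks, or 28 days. With ±7 days at each end it runs from 28 − 14 = 14 days to 28 + 14 = 42 days. Safety follow-up ends 20 weeks after the last dose, so the nominal window is 4/20, one fifth, of that period.

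**Step 4: the size.** If k subjects are recoded out of N, the medication-discontinued percentage rises by 100 × k/N points.

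| k (assumed) | N = 200 (ceiling) | N = 150 (assumed) |
|---|---|---|
| 1 | 0.5 | 0.67 |
| 2 | 1.0 | 1.33 |
| 5 | 2.5 | 3.33 |
| 10 | 5.0 | 6.67 |

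As an illustration, suppose 1% to 3% of 200 subjects (2 to 6) leave between the Week 100 dose and the end of follow-up, spread evenly. Then 2 × 4/20 = 0.4 to 6 × 4/20 = 1.2 subjects fall before Visit 13, which is 0.2 to 0.6 points.

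**Step 5: the direction.** The rule as explained turns a study discontinuation into a medication discontinuation. It contains no step that turns a medication discontinuation into a completion, so the count can only go up.

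**The case against.** The strongest reply is that the tie-break applies only when the two pages are inconsistent. Because SAP 5.1 uses different milestones, a page showing treatment completed and a page showing study discontinued are not inconsistent. The rule may have been meant for terminated subjects with no medication-discontinuation record. That is a reasonable account of the intent, but the text does not say it. The explanatory clause names study discontinuation as the case to override, and the closing parenthesis applies the rule whatever the eCRF reports. A programmer following it literally would recode a subject dosed at Week 100. If the wording is only ambiguous, it needs the same clarification.

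Other points on that side stand and limit the finding:
- A reader might infer that everyone who leaves during the 20-week follow-up is misclassified. Anyone who attended Visit 13 is a study completer by definition. Such a subject is affected only if the termination page still records discontinuation, and the layout of that page is not given.
- The schedule labels Visit 13 jointly as Week 104 and Early Termination, so an early termination visit after the Week 100 dose could arguably count as attending it. That would shrink the group further.
- A reader might infer that the pandemic made this common. SAP 12.6 lists "Termination of study participation" as an impact category, and SAP 10.2.4 expects the pandemic to be ongoing at the last visit. Neither predicts terminations between Weeks 100 and 104.
- It is natural to suppose that the study-withdrawal reason would fill the medication-discontinuation row, but SAP 5.1 does not say so.
- The listings show medication end dates, both sets of discontinuation reasons and every administration, so a careful reader could recover the true status. That softens the error but does not correct the table.

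**Conclusion.** The concern holds in a limited form. SAP 5.1 contains a rule that, read literally, reclassifies a subject who meets its own definition of treatment completion. The certain cases are subjects dosed at Week 100 who leave before Visit 13. Subjects who leave later are affected only if their termination page records discontinuation.

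The size cannot be computed, because the documents do not give the number of such subjects. It is probably small: 0.5 points per subject at N = 200, over a window of about four weeks. Any total, including the illustration above, rests on an assumed number of departures, and no baseline discontinuation rate is available to build on.

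A reader might infer that the trial's safety or tolerability results are biased. The documents do not support that. The primary variables are incidences of TEAEs and serious TEAEs. Withdrawal due to TEAEs is measured from adverse event records and already combines study and medication discontinuation (SAP 2.2.1.2). Exposure and time at risk use dose and contact dates (SAP 10.1). Only the descriptive medication-disposition table and its reasons can change. This is a minor point, worth correcting because it is an internal contradiction and costs almost nothing to remove.

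**What to change.** Add one sentence after the override in SAP 5.1:

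*This override applies only to subjects who did not receive a dose at Visit 12 (Week 100); a subject dosed at Visit 12 is counted as having completed study medication regardless of later study status.*

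The cost is one sentence and one condition in the disposition program. It uses the SAP's existing completer definition and dosing records already collected on the study medication administration page. It needs no new data and changes no study procedure.
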